The biopsychosocial model of pain illustrates that pain is both a sensory and emotional experience (Darnall et al., 2017). Pain has been described as a subjective perception of sensory information that can be influenced by genetics, learned experience, psychological state, and sociocultural influences (Gatchel et al., 2007). Many treatment modalities focus on the sensory or physical aspects of pain, but there is much less emphasis on treating the emotional experience of pain, and pain specific training for health professionals is lacking (Darnall et al., 2017). Emerging studies on interdisciplinary interventions that address the physical, emotional, and cognitive aspects of pain have reported small to medium positive effects (e.g., Bujak et al., 2019; Joypaul et al., 2019). Interventions employing mindfulness training reported small effect sizes for reductions in pain intensity, along with improvements in quality of life, although the quality of evidence analyzed was low (Hilton et al., 2017). A meta-analysis on interventions employing neurophysiological pain education, which uses cognitive behavioural techniques (CBT) to re-conceptualize beliefs about pain, reported small to moderate effect sizes for pain reduction in patients with chronic lower back pain (Tegner et al., 2018). Similarly, moderate effect sizes were found in studies employing CBT in patients with chronic low back pain (Hoffman et al., 2007).

Interventions that focus on pain education, mindfulness training, and CBT do not involve physical manipulations, and as such there is an opportunity to provide care remotely or through online or mobile-application-(app)-based programming. A recent meta-analysis reviewed seven studies on app-based interventions for chronic pain and found significant (albeit small) improvements in pain intensity (Pfeifer et al., 2020). Other online or mobile app-based interventions for chronic pain in elderly and adolescents have reported improvements in pain intensity and emotional functioning (Shaygan & Jaber, 2021) and improvements in awareness of pain response (Berman et al., 2009).

A mobile app informed by the biopsychosocial model of pain that employs a “mind-body” approach was evaluated for quality of self-management support functions specific to chronic pain. Mind-body medicine considers the interactions between the brain and body and considers how emotional, cognitive, and social factors can influence health (e.g., Morone & Greco, 2007). The mind-body app that we explore in the current trial scored the highest of the 19 apps evaluated in both number of self-management functions addressed within the app and scored among the highest in overall app quality as measured by a standardized rating scale (Mobile App Rating Scale) (Devan et al., 2019). To our knowledge, this mobile app has not previously been independently evaluated to determine its efficacy in the treatment of chronic pain. The mind-body app encompasses many of the modalities described above, including

mindfulness training through meditation, CBT through brain training exercises and journaling, and pain education through expert interviews and recorded microlessons. We aimed to investigate the efficacy of the mind-body based mobile app in the treatment of chronic pain using a randomized control trial that involved 6-weeks of regular app usage compared to a usual care, wait-listed control group.

Hypotheses

- i) Participants in the intervention group will report a greater reduction in pain intensity compared to control participants.
- ii) Participants in the intervention group will report improvements in pain catastrophizing, pain interference, and quality of life.
- iii) Changes in pain intensity will be correlated with frequency of app usage.

Objectives:

- i) To investigate the efficacy of a mind-body based mobile app on the experience of chronic pain relative to a waitlisted control group. Outcomes include self-reported measures of pain intensity, perceptions/thoughts about pain, quality of life, and/or functional ability.
- ii) To explore whether frequency of app usage is associated with changes in pain intensity and interference.
- iii) To explore whether changes (if any) in pain intensity and interference persist six weeks post-trial completion.

Primary outcome: Pain intensity as measured using the Brief Pain Inventory (BPI).

Secondary outcomes:

- a. The following additional measures will be compared between the intervention and control group:
 - Pain intensity as measured by the PROMIS Pain Severity short form measures severity over a 7 day time period.
 - Pain interference as measured by the PROMIS Short Form ((PROMIS Health Organization and Cooperative Group, 2012); (Kean et al., 2016).
 - Pain interference as measured by items in the BPI (Cleeland & Ryan, 1994).
 - Thoughts about pain as measured by Pain Catastrophizing Scale (PCS) score (Sullivan et al., 1995).
 - Quality of life as measured by the short-form (SF)-12 (Ware et al., 1996)
 - Depression, anxiety, and stress as measured by the DASS-21 (Lovibond & Lovibond, 1995).
 - Medication use.
- b. The following exploratory analyses will be performed on the intervention group data:
 - Relationship between all outcomes and frequency of app usage in the intervention group.
 - 12-week follow-up analysis (6 weeks post trial end) to determine whether changes (if any) persist.

Methods

Study Design: This is a parallel group randomized control trial. Participants meeting eligibility criteria at pre-trial self-report screening will be invited to participate in the study. Participants who provide informed consent, complete the baseline data collection, and qualify for study inclusion will be randomized to either an intervention group (mind-body app usage for 6-weeks) or a wait-listed control (usual care). Randomization will be stratified on gender and pain intensity.

Participants

Inclusion: Participants aged 18 to 75 years who have non-malignant chronic or persistent pain. Chronic pain is generally defined as persistent pain that has lasted for more than 3 months (Treede et al., 2015). Our study will include participants that have had ongoing pain for at least 6 months, and participants must experience pain at least half the days in the last 6 months (Deyo et al., 2014). Pain can include bodily pain or head pain (migraine/headache). According to the classifications described above by Treede et al., (2015), our study includes participants with primary chronic pain, head/orofacial pain, visceral pain, post-surgical, and musculoskeletal pain.

Exclusions: The following participants are excluded from participation. Self-reported history of any of the following:

- Psychotic illness or manic episode
- Substance use disorder or problematic substance use within 6 months of start date
- Metastasizing cancers
- Cognitive impairment (that could interfere with using the application)
- Previous experience with the mind-body app under study.

Procedures

Participants qualifying for study inclusion will be randomized to either an intervention group (mind-body app) or a control group (usual care, wait-listed). Randomization will be stratified on pain intensity on average (from Brief Pain Inventory, item that inquires about pain intensity on average) and gender. We decided to include gender rather than sex for data collection and randomization. Few clinical trials in Canada collect data based on gender, and there are numerous ways that gender may impact pain experience (Boerner et al., 2018; Welch et al., 2017). Randomization method will involve computer-generated block randomization to create varying block sizes of 4 and 8. We will run the trial in cohorts (run in series) with rolling recruitment. First cohort will start the trial October 15th, 2021 (randomized on October 14th, 2021). The anticipated start date for the second cohort is January, 2022 (randomized immediately before cohort start). If we meet our targeted sample size with two cohorts, we will stop recruitment. If we do not have a sufficient sample, we will run a third cohort in Spring, 2022. Data will not be analyzed until the final cohort has complete the 12-week follow-up.

Intervention: Participants in the intervention group will be provided 6-weeks of free access to a mind-body based app. The app includes activities that are evidence-based and informed to treat

the biopsychosocial model of pain. The app is self-directed and includes activities in brain training (cognitive behavioural therapy), meditation, pain education, and expressive writing (journaling). The app also includes links to podcasts that include interviews with scientific experts in chronic pain, pain psychologists, and recovery stories. At the start of the trial participants will be given a brief (<5 min) introductory video to orient them to the app and provide guidelines and tips. Participants will be asked to engage with the app daily or at minimum 4 times per week. A weekly frequency log (during weeks 2, 3, 4, 5, and 6) will be sent to participants via email (with a link to survey monkey) to record number of times they used the app in the previous 7 days. During the trial, participants are asked to continue with usual care for pain treatments (in addition to app usage).

Control: Participants in the control group will be made aware that they are in the control group as they await access to the app following completion of the trial. They are asked to continue with their usual care for pain treatments over the 6-week trial. A weekly email will be sent to control participants (with a link to survey monkey), to include similar frequency of contact with the research team, and to record any changes (if any) in usual care treatments.

Measures

All participants (control and intervention) will complete baseline questionnaires (detailed below) and a follow-up set of questionnaires at 6 weeks (same as baseline, minus the demographics and pain history sections). All questionnaires and logs will be completed through [surveymonkey.com](https://www.surveymonkey.com). To link pre- and post-surveys along with frequency logs, participants will be given a unique alphanumeric identifier. We will do an additional follow-up survey at 12 weeks in the intervention group. This survey will be similar to the survey at 6 weeks, but will also inquire whether participant continued with app usage.

Measures:

The questionnaires will include the following:

1. Demographics: We will collect data on gender, age, socioeconomic status (education, income), residence, relationship status, dependents, employment status.
2. Pain history: Participants will provide information on their pain condition. This will include location, diagnosis, date of onset, average frequency, changes in employment due to pain. Other details regarding pain are captured in the questionnaires that follow.
3. Brief Pain Inventory Short Form (BPI-SF) - this includes items about location of pain, intensity of pain, current treatments, and interference with daily activities (Cleeland & Ryan, 1994)
4. PROMIS Pain Intensity Scale (Adult Short form) - 3 items (PROMIS Health Organization and Cooperative Group, 2012).
5. PROMIS Pain Interference Scale (Adult Short form) - 8 items (PROMIS Health Organization and Cooperative Group, 2012).
6. Pain Catastrophizing Scale (Sullivan et al., 1995).
8. DASS-21 (Depression, Anxiety, Stress Scale) - 21 items (Lovibond & Lovibond, 1995).
9. QoL questionnaire- SF 12 (Ware et al., 1996).

Data analysis

Power analysis: We estimated a moderate effect size of $f = 0.3$ (Cohen's $d = 0.6$). A meta-analysis of mobile app-based interventions for the treatment of chronic pain (Pfeifer et al., 2020) reported a small effect at Cohen's $d = 0.4$, but the content of the apps was highly variable and not all included pain education and/or CBT exercises. Another meta-analysis on psychological interventions that included CBT compared to wait-listed controls reported a Cohen's $d = 0.62$ (Hoffman et al., 2007). Using G-power (Erdfelder et al., 2009) calculation with an estimated power of $f = 0.3$, a sample size of $n = 90$ would be required to achieve 80% power (at $alpha = .05$). We aimed to enroll $n = 100$ participants in total.

Statistical analysis: Data will be analyzed using repeated measures analysis of co-variance (ANOVA) with baseline data as a covariate, intervention vs. control as between-group factors, and variable of interest (e.g., pain intensity) as the dependent variable for the primary analysis. It is recommended that randomized controlled trials employ ANCOVA rather than paired t-tests or repeated measures ANOVA (Egbewale et al., 2014).

References

- Berman, R. L. H., Iris, M. A., Bode, R., & Drengenberg, C. (2009). The Effectiveness of an Online Mind-Body Intervention for Older Adults With Chronic Pain. *Journal of Pain*, *10*(1), 68–79. <https://doi.org/10.1016/j.jpain.2008.07.006>
- Boerner, K. E., Chambers, C. T., Gahagan, J., Keogh, E., Fillingim, R. B., & Mogil, J. S. (2018). Conceptual complexity of gender and its relevance to pain. In *Pain* (Vol. 159, Issue 11, pp. 2137–2141). Lippincott Williams and Wilkins. <https://doi.org/10.1097/j.pain.0000000000001275>
- Bujak, B. K., Regan, E., Beattie, P. F., & Harrington, S. (2019). The effectiveness of interdisciplinary intensive outpatient programs in a population with diverse chronic pain conditions: a systematic review and meta-analysis. *Pain Management*, *9*(4). <https://doi.org/10.2217/pmt-2018-0087>
- Cleeland, C. S., & Ryan, K. M. (1994). Pain assessment: global use of the Brief Pain Inventory. In *Annals of the Academy of Medicine, Singapore* (Vol. 23, Issue 2).
- Darnall, B. D., Carr, D. B., & Schatman, M. E. (2017). Ethics forum: Pain psychology and the biopsychosocial model of pain treatment: Ethical imperatives and social responsibility. In *Pain Medicine (United States)* (Vol. 18, Issue 8, pp. 1413–1415). Oxford University Press. <https://doi.org/10.1093/pm/pnw166>

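### Randomisation is stratified on gender and BPI average pain, but the analysis model does not name either factor; adding them is a small, nearly free improvement

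*Combined protocol and SAP*

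**What the plan says.** Stratification is stated twice. Methods, Study Design: "Randomization will be stratified on gender and pain intensity". Procedures is more specific: "Randomization will be stratified on pain intensity on average (from Brief Pain Inventory, item that inquires about pain intensity on average) and gender". Allocation is by permuted blocks: "Randomization method will involve computer-generated block randomization to create varying block sizes of 4 and 8". The plan gives a reason for the gender factor: "We decided to include gender rather than sex for data collection and randomization", because "there are numerous ways that gender may impact pain experience".

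Data analysis, Statistical analysis, contains the only between-arm model. It is an ANCOVA "with baseline data as a covariate, intervention vs. control as between-group factors", with the "variable of interest (e.g., pain intensity) as the dependent variable for the primary analysis". It does not say which baseline data are meant, and it mentions neither gender, the pain stratum nor the stratification. Gender is collected at baseline (Measures, Demographics), as is the BPI.

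**The concern.** A factor that was thought important enough to constrain allocation would normally also appear in the analysis. Stratified allocation balances the factor between arms. If the model then leaves it out, any variation it explains beyond the other covariates stays in the error term. The reported standard error does not credit the balance that the design achieved, so the confidence interval is too wide and the test conservative.

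The gap differs by outcome. For the primary BPI pain outcome, the baseline term largely covers the pain stratifier, so the missing factor is gender. For non-pain secondary outcomes (PCS, DASS-21, SF-12), the outcome's own baseline stands in for neither stratifier.

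Leaving the covariates unnamed also leaves open whether gender is adjusted for and how rare gender categories are handled. Either choice could be made after the data are seen.

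**Working it through.** **The plan's own figure.** With f = 0.3, two-sided alpha 0.05 and a two-arm ANCOVA with one covariate, the noncentral F calculation (1 numerator df, noncentrality f²N, denominator df N − 3) gives power 0.7991 at N = 89 and 0.8036 at N = 90. The stated N = 90 reproduces. At the enrolment target ("We aimed to enroll $n = 100$ participants in total"), power before dropout is 0.8438.

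**Inputs.** From the documents: d = 0.6, N = 90 and 100, alpha 0.05, blocks of 4 and 8. Assumed: 1:1 allocation, d on the baseline-adjusted residual scale, the gender split p, and the gender gap g in residual SDs. The documents give neither p nor g, so a range is shown.

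**Formulas, primary outcome, exact balance.**
- Share of residual variance due to gender: R = g²p(1 − p).
- Overstatement of the standard error: k − 1, with k = 1/√(1 − R).
- Type I error without gender: 2·P(T > k·t), with t the critical value on N − 3 df.
- Power without gender: P(T′ > k·t) on N − 3 df. Power with gender: P(T′ > t₁), with t₁ the critical value on N − 4 df. T′ is noncentral t with noncentrality k·0.6·√N/2.

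**One case in full** (N = 90, p = 0.8, g = 0.3). R = 0.09 × 0.16 = 0.0144. k = 1/√0.9856 = 1.0073. The effective critical value is 1.9876 × 1.0073 = 2.002, so type I error is 4.84%. The noncentrality is 0.6 × √90/2 = 2.846, times k = 2.867. Power is 80.5% without gender and 80.9% with it.

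| Split | Gap (SD) | R | SE too wide | Type I error | Power without | Power with | Gain (points, before rounding) |
|---|---|---|---|---|---|---|---|
| 80/20 | 0.2 | 0.64% | 0.3% | 4.93% | 80.4% | 80.6% | 0.17 |
| 80/20 | 0.3 | 1.44% | 0.7% | 4.84% | 80.5% | 80.9% | 0.38 |
| 80/20 | 0.43 | 3% | 1.5% | 4.67% | 80.7% | 81.5% | 0.81 |
| 80/20 | 0.56 | 5% | 2.6% | 4.45% | 81.0% | 82.3% | 1.36 |
| 50/50 | 0.2 | 1% | 0.5% | 4.89% | 80.5% | 80.7% | 0.26 |
| 50/50 | 0.3 | 2.25% | 1.1% | 4.75% | 80.6% | 81.2% | 0.61 |

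The 3% and 5% rows are optimistic for gender. At N = 100 with an 80/20 split, power without and with gender is 84.5 and 84.6% (gap 0.2), and 84.6 and 84.9% (gap 0.3).

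**Simulation** (N = 90, 40,000 replicates, blocks of 4 and 8 within gender and two pain strata cut at the median; Monte Carlo standard error of the paired power difference 0.05 to 0.09 points).
- Primary outcome, adding gender: −0.07, +0.07 and +0.42 points at gaps of 0, 0.2 and 0.3 SD. At 0.3 SD the spread of the estimate is 0.2095 with or without gender, so the gain is in the reported standard error and not in true precision. Under the null at that gap, type I error is 4.92% without gender and 5.10% with it.
- A third gender category of 3% (about 3 of 90) with its own term: −0.32, −0.26 and 0.00 points at gaps of 0, 0.2 and 0.3 SD. Pooled: +0.14 and +0.32 at 0.2 and 0.3 SD.
- Secondary outcome, adding gender and BPI average pain: −0.36 points if neither is prognostic; +0.20 with a gap of 0.2 SD and partial correlation 0.1; +1.48 with 0.3 SD and 0.2.

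A separate simulation with deliberately strong effects of both factors on a secondary outcome put the standard error about 10% too wide, type I error at 3.7%, and power at 69.5% without the factors against 76.2% with them. That is an upper bound, not an expectation.

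**The case against.** The strongest reply is that nothing turns on this. ANCOVA on the outcome's baseline is valid without the stratifiers, the error is on the safe side, and at plausible gender gaps the primary-outcome gain is a few tenths of a point, partly within simulation noise. The sizes rest wholly on assumed inputs. That all stands, and it is why the point is minor.

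A second reply is that the covariate phrase is undefined and could be meant to include gender, which is in the baseline questionnaire. That questionnaire also holds age, income, education, residence, pain history and every scale. Read that widely, the covariate set is unspecified; read narrowly, the stratifiers are absent. Both readings call for the covariates to be named.

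Third, the remedy has limits. It costs a little power if the factors are not prognostic, and a rare gender category with its own term cancels the gain. Each cohort is randomised separately, so the two stratifiers do not describe the whole allocation scheme. No cut-points are given for the pain strata. Medication use has no stated scale, so a linear model may not suit it. For PROMIS pain intensity, BPI average pain is likely to add little. These points bear on how the fix is worded; they do not make it wrong.

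Last, it may seem inconsistent to deny type I error inflation and also warn about choices made after seeing the data. The first statement concerns a pre-specified model without the stratifiers. The second concerns leaving the model open, and that risk is not quantified here.

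**Conclusion.** The concern holds, as a minor one. On the natural reading, gender is in no between-arm model and BPI average pain is absent from the models for the non-pain secondary outcomes. The consequence is a slightly wide standard error and a slightly conservative test, without bias, without inflated type I error and without any change to N = 90. For the primary outcome, the standard error is 0.3 to 0.7% too wide and power 0.2 to 0.4 points lower, assuming an 80/20 split, a gender gap of 0.2 to 0.3 SD after baseline adjustment, and d = 0.6 on the residual scale. For a non-pain secondary outcome, adding both factors changes power by about −0.4 to +1.5 points over the moderate settings examined. The main value of the change is that the analysis follows the stratification and the covariates are fixed in advance.

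**What to change.** Replace the undefined covariate phrase with a named list. For each between-arm outcome: arm, the baseline value of that outcome, gender coded as in the randomisation, and baseline BPI average pain. For the primary BPI pain outcome the baseline term largely covers the pain stratum, so gender is the term to add.

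In the same sentence, state three details:
- a rule, written before data are analysed, for pooling sparse gender categories;
- whether BPI average pain enters as a score or as strata, with cut-points if strata;
- whether cohort is a term, since cohorts are randomised separately.

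If the stratifiers are to be left out, say so and why.

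The cost is wording only, since both variables are already collected at baseline. If the factors turn out not to be prognostic, the loss is about 0.1 power points for the primary outcome with sparse categories pooled, about 0.3 if a 3% category keeps its own term, and about 0.4 for a secondary outcome with both terms.

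### Participants are randomised in serial cohorts, but the week-6 model has no cohort term, which costs a little precision without biasing the arm contrast

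*Combined protocol and SAP*

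**What the plan says.** Procedures sets out a batch design: "We will run the trial in cohorts (run in series) with rolling recruitment". The first batch is dated exactly: "First cohort will start the trial October 15th, 2021 (randomized on October 14th, 2021". The second follows the same pattern: "The anticipated start date for the second cohort is January, 2022 (randomized immediately before cohort start". A third is planned for Spring 2022 only if the sample falls short.

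Study Design names the strata: "Randomization will be stratified on gender and pain intensity". Procedures repeats them, specifies blocks of 4 and 8, and does not say whether the block lists restart with each cohort. Under Statistical analysis, the model has the baseline value as covariate and "intervention vs. control as between-group factors". Cohort does not appear in the analysis section.

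Under Measures, both arms complete baseline and week 6, but only the intervention group is surveyed at 12 weeks. The secondary outcomes list labels that 12-week analysis exploratory.

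**The concern.** Cohort is the batch in which people are actually randomised, and each batch is assessed in its own calendar window. If outcome levels differ between batches by more than baseline adjustment absorbs, a model without cohort counts that difference as noise. Randomisation within each batch has already largely removed it from the arm contrast, so the model reports a standard error larger than the true sampling variability. The effect estimate is unaffected. What is at stake is some power and wider intervals than the design warrants, in a trial with a target of only 100 people.

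**Working it through.** **Inputs from the documents.** f = 0.3 (d = 0.6), alpha 0.05, 80% power, required N = 90 and target N = 100 (Power analysis); blocks of 4 and 8, and serial cohorts (Procedures); strata of gender and BPI average pain (Study Design, Procedures).

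**Inputs assumed.** 1:1 allocation, two cohorts of 50, four strata with shares 40/40/10/10%, baseline-outcome correlation 0.5, no dropout, and a residual cohort shift of 0 to 1.0 SD in outcome.

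**1. The plan's own figure.** A two-group F test with noncentrality N × f² = 90 × 0.09 = 8.1 has power 0.804, and 90 is the smallest N that reaches 0.80. At N = 100 the power is 0.844. The stated sample size reproduces.

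**2. Is the arm contrast biased?** In cohort 1 both arms run from 15 October to 26 November 2021 (42 days), so a calendar effect reaches both alike. Simulation (2,500 runs per setting, blocks restarted per cohort, no cohort term) gave mean estimates of 0.000 to 0.002 when the true d was 0, and 0.596 to 0.605 when it was 0.6, over all cohort shifts. There is no systematic bias.

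Chance imbalance is small. With equal cohorts, the displacement is the cohort shift times the between-cohort difference in treated share. The SD of that difference was about 0.032 if lists restart and 0.050 if they run on. At a 0.5 SD shift the typical displacement is 0.5 × 0.032 = 0.016 SD to 0.5 × 0.050 = 0.025 SD, against a standard error of about 0.18 SD.

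**3. How much is the standard error inflated?** Residual variance after baseline is 1 − 0.5² = 0.75. An unmodelled shift s between two equal cohorts adds s²/4. The reported standard error is therefore 2 × √[(0.75 + s²/4)/100]:

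| Shift (SD) | Without cohort term | With cohort term |
|---|---|---|
| 0 | 0.173 | 0.173 |
| 0.2 | 0.174 | 0.173 |
| 0.5 | 0.180 | 0.173 |
| 1.0 | 0.200 | 0.173 |

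The simulated mean standard errors agree: 0.181 and 0.201 without the term at 0.5 and 1.0 SD, and 0.173 to 0.174 with it.

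**4. Effect on the test** (simulation, blocks restarted):

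| Shift (SD) | Type I error, without → with | Power at d = 0.6, without → with |
|---|---|---|
| 0 | 0.046 → 0.047 | 0.924 → 0.922 |
| 0.3 | 0.056 → 0.061 | 0.919 → 0.923 |
| 0.5 | 0.043 → 0.049 | 0.916 → 0.930 |
| 1.0 | 0.026 → 0.052 | 0.862 → 0.927 |

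With 2,500 runs, Monte Carlo error is about half a point in each entry. Letting the lists run on across cohorts gave the same picture (0.922 → 0.933 at 0.5 SD; 0.865 → 0.928 at 1.0 SD). Three cohorts of 40, 35 and 25 with 0.5 SD steps gave 0.891 → 0.925. Power exceeds 0.844 here because baseline is assumed to explain a quarter of the variance.

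**5. Without that help from baseline.** Take correlation 0 and N = 90, the plan's own 80% setting. The true SD of the estimate is 2/√90 = 0.211, and the reported standard error is 2 × √[(1 + s²/4)/90], which is 0.217 at s = 0.5 and 0.236 at s = 1.0. Using power ≈ Φ[(0.6 − 1.988 × SE)/0.211], power is about 0.79 and 0.73 without the term, against about 0.80 with it. The losses are about 2 and 7 points, of similar size to step 4.

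**6. The 12-week change.** About 50 treated participants with correlation 0.5 give a standard error of √[2 × (1 − 0.5)/50] = 0.14 SD. There is no control at that visit, so a calendar shift of an assumed 0.1 to 0.3 SD enters in full: 0.1/0.14 = 0.7 to 0.3/0.14 = 2.1 standard errors. A cohort term separates cohorts from one another but cannot remove a trend common to an uncontrolled arm.

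**The case against.** The strongest reply is that this is preference rather than error. Randomisation within each cohort already protects the comparison, and the plan adjusts for a baseline measured in the same cohort, which absorbs part of any wave or season difference. The documents give no reason to expect a large residual shift. All of this stands, and it is why the point is minor. It does not remove the precision argument: the term costs almost nothing and protects power if a shift does occur.

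Three stronger readings are tempting, and the documents do not support them.

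- A reader might infer that season or recruitment wave confounds the arm contrast. Each cohort has concurrent controls, and step 2 shows no bias.
- A reader might infer that block lists carry over between cohorts and unbalance the arms. The plan does not say so, and randomising each batch immediately before its start fits fresh lists at least as well. Imbalance in the first cohort comes from incomplete final blocks and is the same under either scheme.
- A reader might expect a cohort term to rescue the 12-week persistence result. It cannot, for the reason in step 6. A by-cohort table would be descriptive only: with about 25 treated people per cohort, the standard error of the difference between two cohorts' changes is √(2 × 1/25) = 0.28 SD, too wide to show or exclude plausible inconsistency.

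**Conclusion.** The point holds as a minor matter of precision. The planned week-6 model omits the batch in which participants are randomised. The estimate stays unbiased, and the test is valid but slightly conservative. The loss is essentially nil at a residual cohort shift of 0.2 SD or less, about 1 power point at 0.5 SD, and 6 to 7 points at 1.0 SD, where type I error falls to about 0.026. These figures rest on two cohorts of 50, a baseline-outcome correlation of 0.5, no dropout and shifts chosen for illustration, since the documents supply none of them. The lack of a control group at 12 weeks is a real limitation on an exploratory result, but a separate one.

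**What to change.** Under Statistical analysis, add cohort as a fixed effect to the week-6 between-group ANCOVA for each outcome, alongside baseline and arm. With two or three cohorts this uses 1 to 2 degrees of freedom out of about 90 and needs no new data. Procedures defers all analysis until the last cohort has finished its 12-week follow-up, so the term can be specified before any outcome is analysed. For the record, state in one sentence whether block lists restart with each cohort. If 12-week changes are tabulated by cohort, describe the table as descriptive and do not present it as a control for calendar effects.

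### The weekly app-use logs capture at most 35 of the 42 days of access; one added usage item would close the gap in the exploratory usage analyses at almost no cost

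*Combined protocol and SAP*

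**What the plan says.** The Intervention paragraph under Procedures states: "Participants in the intervention group will be provided 6-weeks of free access to a mind-body based app". The same paragraph sets out how use is recorded: "A weekly frequency log (during weeks 2, 3, 4, 5, and 6) will be sent to participants via email", with a survey link "to record number of times they used the app in the previous 7 days". It does not give the day of the week on which a log goes out.

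The Measures section describes two later surveys. At the end of the trial there is "a follow-up set of questionnaires at 6 weeks (same as baseline, minus the demographics and pain history sections", and the numbered list of questionnaires has no app-use item. The 12-week survey, sent to the intervention arm only, "will also inquire whether participant continued with app usage". Server or analytics data are not mentioned.

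The log data serve hypothesis iii, "Changes in pain intensity will be correlated with frequency of app usage", together with objective ii and the exploratory analysis of every outcome listed in part b of the secondary outcomes. The Statistical analysis paragraph does not say how the logs are turned into an exposure variable.

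**The concern.** Change in pain is measured over six weeks, whereas the exposure set against it is measured over five. The sending day is not given, so a reader cannot tell whether the first week, the last week or parts of both go unrecorded. A participant whose use is constant loses nothing, because the missing week only changes the scale. Where use varies from week to week, the five-week mean is a noisy stand-in for the six-week mean, and a correlation with outcome is weakened.

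What is at stake is some precision in an exploratory analysis. It is worth raising because a week that was not asked about cannot be recovered from these logs afterwards.

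**Working it through.** The plan gives no figure of its own on this point, so there is none to reproduce.

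**Coverage.** Inputs from the Intervention paragraph: 6 × 7 = 42 days of access, five logs (weeks 2 to 6), seven-day recall. Maximum coverage is 5 × 7 = 35 days, or 83.3%, leaving 7 days (16.7%). If each log goes out at the start of day *d* of its week (*d* = 8 meaning the end of the week), the five windows run from day *d* to day *d* + 34. They miss *d* − 1 days at the start and 8 − *d* at the end, always 7 in total.

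- First day of the week (*d* = 1): days 1–35 covered, days 36–42 missed.
- End of the week (*d* = 8): days 8–42 covered, days 1–7 missed.
- Mid-week: the 7 missed days are split between the two ends.

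Adding a seven-day item at the end of week 6 (days 36–42) gives 43 − *d* distinct days, with *d* − 1 days counted twice. That is 42 days with no overlap at *d* = 1, 41 down to 36 days for *d* = 2 to 7, and no gain (35) at *d* = 8. At *d* = 8 a log at the end of week 1 gives 42 instead.

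**Cost under full response.** The documents give none of the following inputs. Assumed: weeks exchangeable with between-week correlation *r*; a true correlation of 0.30 between outcome change and six-week mean use; 50 analysed participants (100 split 1:1); two-sided 5% test; counts reported without error.

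Correlation of five- with six-week mean: (5 + 25*r*) / √[(5 + 20*r*)(6 + 30*r*)]. At *r* = 0.1 this is 7.5/√(7 × 9) = 0.945.

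Power by Fisher's z, with ρ = 0.30 times that correlation: Φ(√47 · atanh ρ − 1.96), the opposite tail being negligible. With all six weeks: √47 × 0.3095 − 1.96 = 0.162, so 56.4%.

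| *r* | Five- v six-week correlation | Power, five weeks | Loss from 56.4% (points) |
|---|---|---|---|
| 0.1 | 0.945 | 51.5% | 4.9 |
| 0.3 | 0.973 | 54.0% | 2.4 |
| 0.5 | 0.986 | 55.2% | 1.2 |
| 0.7 | 0.993 | 55.8% | 0.6 |
| 0.9 | 0.998 | 56.3% | 0.1 |

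**Cost with unreturned logs.** Assume each log comes back with probability *p*, independently of use, and the exposure is the mean over the *k* returned reports. Its correlation with the true six-week mean is √{[(1 + 5*r*)/6] / E[(1 + (*k* − 1)*r*)/*k*]}. As planned, *k* is binomial(5, *p*) given at least one. If the sixth item sits in the 6-week survey, *k* is 1 + binomial(5, *p*), because a participant with a 6-week change score has returned that survey (item non-response ignored).

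Example, *p* = 0.8 and *r* = 0.1: the numerator is 1.5/6 = 0.25. The expectation is 0.3415 as planned and 0.2875 with the sixth item, so the correlations are √(0.25/0.3415) = 0.856 and √(0.25/0.2875) = 0.933. Power goes from 43.7% to 50.4%.

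| *r* | Power, *p* = 0.9 | Gain | Power, *p* = 0.8 | Gain |
|---|---|---|---|---|
| 0.1 | 47.9 → 53.6% | 5.7 | 43.7 → 50.4% | 6.7 |
| 0.3 | 52.1 → 55.1% | 3.0 | 49.7 → 53.5% | 3.8 |
| 0.5 | 54.2 → 55.7% | 1.5 | 52.8 → 54.9% | 2.1 |
| 0.7 | 55.3 → 56.1% | 0.8 | 54.7 → 55.7% | 1.0 |
| 0.9 | 56.1 → 56.3% | 0.2 | 55.9 → 56.2% | 0.3 |

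Gains are differences of the rounded powers. All six reports would exist for 0.9⁵ = 59% or 0.8⁵ = 33% of analysed participants, so an exposure that needs a complete total would discard many of them; a mean over returned reports would not.

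**The case against.** The plan promises a frequency of use, not a six-week total. Five weekly samples give a legitimate rate, and the six-week mean is a benchmark brought in here. If logs go out at the start of each week, exposure also ends before the outcome is measured, which is a defensible ordering. On the figures above the loss is slight, and under full response it is below one point once between-week correlation reaches 0.7. Nothing in the documents favours a low value.

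Most of this stands, and it limits the point to a minor one. It does not remove the gain: asking about the sixth week improves the measure, and an analyst who prefers exposure to precede outcome can still use weeks 1 to 5.

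A second objection also stands. The logs are emailed links with no stated completion window. If respondents count seven days back from the day they answer, late replies shift the windows. Full 42-day coverage therefore holds only if each item names its dates or is answered promptly.

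A reader might infer that the trial loses its opening week, that hypothesis iii cannot be tested, or that the efficacy result is compromised. The documents support none of these. The sending day is not stated, the five-week measure stays close to the six-week one under the assumptions used, and the between-group comparison does not use the logs.

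**Conclusion.** The coverage gap is certain: at most 35 of 42 days, with no other usage count described. Its consequence is small and confined to hypothesis iii, objective ii and the exploratory analysis of outcomes against use. Under full response it costs about 0.1 to 4.9 power points. With logs returned at 80% or 90%, the sixth item recovers about 0.2 to 6.7 points.

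These sizes rest on assumed values of the between-week correlation, the return rate and the true correlation, and on exchangeable weeks, error-free counts and non-response unrelated to use. The loss could be larger if participants' use changes systematically in the unrecorded week. This is an inexpensive improvement that the sponsor could make, not a correction that the trial depends on.

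**What to change.** 1. Send each log on the first day of weeks 2 to 6, and add the same usage-count item to the intervention arm's 6-week survey. If logs must go out at the end of each week, add a week-1 log instead. Avoid mid-week sending, where one extra 6-week item leaves days uncovered and counts others twice.
2. Have every item name the calendar dates it covers, so that a late reply does not move the window.
3. Define the exposure as mean weekly frequency over the returned reports from all six weeks, and report how many each participant returned. The mean overstates use if people who stop using the app also stop replying.

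Cost: one survey item for about 50 participants (assuming 1:1 allocation of the 100 planned), plus a sentence each on sending day, dates and exposure definition. No new linkage is needed, since the plan already provides for it: "To link pre- and post-surveys along with frequency logs, participants will be given a unique alphanumeric identifier". The week-1 alternative adds one contact per arm, because the control arm's weekly email is meant "to include similar frequency of contact with the research team" and should be matched.
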